10.4 Definitions

Treatment Failure: Responses that should be considered clinically beneficial include CR and PR; all others (e.g., stable disease, non-response, PD, death from any cause) should be rated as a treatment failure.

Overall Survival (OS): Defined as the time from first treatment day to death due to any cause, or censored at date last known alive.

Progression-Free Survival (PFS): Defined as the time from first treatment day to the earlier of progression or death due to any cause. Participants alive without disease progression are censored at date of last disease evaluation.

Event-Free Survival (EFS): Defined as the interval between the first treatment day to the first sign of disease progression or start of a new treatment or withdrawal from the trial because of toxicity or death (whichever occurs first).

Time to Next Treatment (TTNT): Defined as the interval between the first treatment day until the patient starts an alternative therapy for progressive CLL.

Relapse: Defined as evidence of disease progression in a patient who has previously achieved the above criteria of a CR or PR for ≥ 6 months.

Refractory Disease: Defined as treatment failure or as progression within 6 months from the last dose of therapy.

Minimal Residual Disease (MRD)-Negative: Blood or marrow with < 1 CLL cell per 10,000 leukocytes assessed by at least four color flow cytometry (MRD flow), allele-specific oligonucleotide PCR, or high-throughput sequencing using the ClonoSEQ assay.

Complete Remission with incomplete marrow recovery (CRi): Some patients fulfill all the criteria for a CR, but have a persistent anemia, thrombocytopenia or neutropenia apparently unrelated to CLL, but related to drug toxicity. These patients should be considered as a different category of remission, CR with incomplete marrow recovery (CRi). The marrow evaluation should be performed with scrutiny and not show any clonal disease infiltrate.

10.5 Response Review

Confirmation of scan results will be reviewed centrally by the Tumor Imaging Metrics Core (TIMC) at DF/HCC, however treatment decisions may be made based on local scan interpretation.

11. DATA REPORTING / REGULATORY REQUIREMENTS

Adverse event lists, guidelines, and instructions for AE reporting can be found in **Section 7.0** (Adverse Events: List and Reporting Requirements).

11.1 Data Reporting

11.1.1 Method

The Office of Data Quality (ODQ) will collect, manage, and perform quality checks on the data for this study.

11.1.2 Responsibility for Data Submission

Investigative sites within DF/HCC or DF/PCC are responsible for submitting data and/or data forms to the Office of Data Quality (ODQ) in accordance with DF/HCC policies.

11.2 Data Safety Monitoring

The DF/HCC Data and Safety Monitoring Committee (DSMC) will review and monitor toxicity and accrual data from this study. The committee is composed of medical oncologists, research nurses, pharmacists and biostatisticians with direct experience in cancer clinical research. Information that raises any questions about participant safety will be addressed with the Sponsor-Investigator and study team.

The DSMC will review each protocol up to four times a year with the frequency determined by the outcome of previous reviews. Information to be provided to the committee may include: up-to-date participant accrual; current dose level information; DLT information; all grade 2 or higher unexpected adverse events that have been reported; summary of all deaths occurring within 30 days of intervention for Phase I or II protocols; for gene therapy protocols, summary of all deaths while being treated and during active follow-up; any response information; audit results, and a summary provided by the study team. Other information (e.g., scans, laboratory values) will be provided upon request.

11.3 Multi-Center Guidelines

This protocol will adhere to DF/HCC Policy MULTI-100 and the requirements of the DF/HCC Multi-Center Data and Safety Monitoring Plan. The specific responsibilities of the Sponsor-Investigator, Coordinating Center, and Participating Institutions and the procedures for auditing are presented in **Appendix C**.

12. STATISTICAL CONSIDERATIONS

12.1 Study Design

An open label, non-randomized phase 2 trial assessing the combination of acalabrutinib, umbralisib, and ublituximab in adult participants with chronic lymphocytic leukemia (CLL). Participants will be enrolled to one of two treatment cohorts:

- **Cohort 1:** Participants with relapsed disease
- **Cohort 2:** Participants who are treatment naïve

Each cohort will follow a one-stage enrollment design, accruing a maximum of 30 participants.

12.2 Sample Size, Accrual Rate and Study Duration

A total of 30 participants will be accrued to each cohort, for a maximum total of 60 participants. The anticipated overall accrual rate is approximately 4 patients per month, for a planned accrual duration of about 15 months. Participants will receive treatment for 24 cycles (2 years) and will continue to be followed for a maximum of 5 years following treatment discontinuation for survival, for a total study length of approximately 8 years.

Table 25: Accrual Targets					
Ethnic Category	Sex/Gender				
	Females		Males		Total
Hispanic or Latino	1	+	3	=	4
Not Hispanic or Latino	20	+	36	=	56
Ethnic Category: Total of all subjects	21	(A1)	+ 39	(B1) =	60 (C1)
Racial Category					
American Indian or Alaskan Native	0	+	0	=	0
Asian	1	+	1	=	2
Black or African American	1	+	3	=	4
Native Hawaiian or other Pacific Islander	0	+	0	=	0
White	19	+	35	=	54
Racial Category: Total of all subjects	21	(A2)	+ 39	(B2) =	60 (C2)
	(A1 = A2)		(B1 = B2)		(C1 = C2)

12.3 Interim Monitoring Plan

The triplet combination of umbralisib, ublituximab, and the BTK inhibitor ibrutinib has been previously tested in this patient population with an acceptable safety profile.¹⁶ Acalabrutinib is a second-generation FDA approved BTK inhibitor that is typically better tolerated by patients and has fewer off-target side effects than ibrutinib (note that a direct head-to-head study has

not been performed).²² This trial will substitute acalabrutinib for ibrutinib to test efficacy of the combination.

If in the first 10 participants who receive at least one cycle of triple therapy with acalabrutinib, umbralisib, and ublituximab, 3 or more develop serious toxicity, this will trigger a consultation with the DSMC about stopping accrual (see **Section 12.2**). Toxicities would include the following events that occur during the first cycle of triple therapy, unless they are clearly due to underlying disease or extraneous causes: grade 4 or higher infusion-related reaction, grade 4 or higher infection, or any other grade 3 or higher, clinically significant, non-hematologic toxicity, except asymptomatic laboratory abnormalities or nausea/vomiting/diarrhea that improves with supportive care. With this design, the probability of triggering a consultation is 0.07 if the true but unknown rate of serious toxicity is 10%, 0.18 if the rate is 15%, 0.74 if the rate is 35%, and 0.83 if the rate is 40%.

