2. BACKGROUND

2.1 Study Disease and Rationale

CLL is the most common leukemia in Western countries, with about 19,000 new cases per year in the US. Most patients are over 70 years old at diagnosis, and over 75 when first treated. At this age multiple comorbidities and prescription medications are common, thereby limiting treatment choices in this population and making time-limited oral therapy for CLL appealing.²

CLL patients are divided according to their prognostic factors, and specifically, by the mutation status of the immunoglobulin heavy-chain rearrangement (*IGHV*), chromosomal abnormalities, and specific somatic mutations. Patients with deletion of the short arm of chromosome 17 (del17p) and/or a mutated *TP53* are at the highest risk. They tend to have more steadily progressing disease, a shorter interval before first therapy and a reduced response rate to standard chemoimmunotherapy (CIT).³ Patients with unmutated *IGHV* also have a more rapid progression to therapy than those with mutated *IGHV*, typically with good response but with continuous relapse and reduced durability after chemoimmunotherapy.

Treatment, especially for older patients or those with any of the higher risk markers, is increasingly based on novel targeted therapies, mainly Bruton tyrosine kinase (BTK) and PI3K inhibitors, that usually at least partially overcome these poor prognostic factors. Although most CLL patients respond to these targeted agents, in both the first line and relapsed setting the CR rate is modest (about 10%) and the drugs are given indefinitely.^{4,5} MRD-negativity, which is an independent predictor for survival in CLL after CIT or venetoclax, is seldom achieved with BCR inhibitor monotherapy.⁶ Moreover, each drug has its own unique toxicity profile, in part due to off-target effects.⁷ Ibrutinib, the first FDA approved BTK inhibitor and most widely used targeted small-molecule-agent in CLL, increases bleeding risk (up to 5% high-grade bleeding) and the incidence of atrial fibrillation (up to 16% at 18 months) and hypertension (25% and rising at 36 months).⁸ Idelalisib, a first-generation PI3K δ inhibitor, has a characteristic autoimmune toxicity profile, mainly colitis, hepatitis and pneumonitis.^{5,9}

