Most frequent drug-related adverse events (AE's) reported were infusion related reactions (IRR) (75% of the patients, including 33% of patients with Grade 3 IRR). Other Grade 3/4 AE's > 10% included: neutropenia (67%) and increase ALT/AST (17%). All AEs were reversible spontaneously or with supportive care intervention. None of the reported adverse events were considered as a dose-limiting toxicity according the judgment of the study Safety Committee. Therefore, the maximum tolerated dose was not reached in this study. Significant blood lymphocyte depletion was observed in all patients: median lymphocyte count at baseline was 46.6 ($\times 10^9/l$); after 1 month (M1) = 1.5 ($\downarrow 94\%$); M4=1.4 ($\downarrow 91\%$) and M6=2.0 ($\downarrow 89\%$). No cases of serum anti-ublituximab antibodies were detected at any time point.

Clinical response was based on the criteria established by the National Cancer Institute (NCI)-Working Group updated in 2008. All patients but one received the planned 8 infusions without any dose reduction--one patient was prematurely withdrawn due to a concomitant secondary leukemia unrelated to ublituximab therapy. Response was evaluated at month 4 for the 11 evaluable patients, with an initial response rate of 64% (7/11) with a confirmed response at month 6 in 5/11 patients (45%) patients (all PRs). Four of the 11 patients achieved stable disease. At the 1 year follow-up, no responders had progressed, demonstrating all confirmed responses were durable despite no ublituximab maintenance therapy. The median progression-free survival (PFS) was not reached at the 12 month follow-up.³⁰

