Liver Toxicity Includes: ALT (SGPT), AST (SGOT), Bilirubin increased	Grade 2	
Assess concomitant medications and risk factors.³
 
First Occurrence: Maintain current dose and schedule of umbralisib, acalabrutinib, and ublituximab (if applicable).
 
Begin supportive care (prednisone 0.5 – 1.0 mg/kg/day or equivalent per treating investigator's discretion).⁴
 
Monitor liver function laboratories at least weekly until Grade 1 or baseline. Once resolved to Grade 1 or baseline, taper prednisone by 10 mg per week until off.
 
If liver toxicity recurs:
 
 • Re-initiate steroids. • Delay umbralisib and ublituximab dosing. • Monitor liver function labs at least weekly until resolution to Grade 1 or baseline. • Once resolved to Grade 1 or baseline, restart umbralisib at current dose and resume ublituximab at full dose and schedule. • Taper prednisone by 10 mg per week until off.

Table 12: Non-Hematologic Toxicity Management		
Event Terms	CTCAE Grade	Study Agent Management Guidelines ¹
Liver Toxicity Includes: ALT (SGPT), AST (SGOT), Bilirubin increased	Grade ≥ 3	
Assess concomitant medications and risk factors.³
 
Hold dosing of umbralisib, ublituximab, and acalabrutinib.
 
Begin supportive care (prednisone 0.5 – 1.0 mg/kg/day or equivalent per treating investigator's discretion).⁴
 
Monitor liver function labs at least weekly until Grade 1 or resolution to baseline. Once resolved to Grade 1 or baseline, resume dosing with study agents, beginning with acalabrutinib and adding umbralisib and ublituximab (as applicable) one week later if the liver toxicity does not return upon re-introduction of acalabrutinib. Reduce dose of umbralisib by one dose level, resume full dose and schedule of acalabrutinib and ublituximab. Taper prednisone by 10 mg per week until off.

Any other non-hematologic toxicity	\leq Grade 2	
No change in study agent dosing or schedule.⁵ Implement supportive care as appropriate.
 
NOTE: If persistent grade 2 diarrhea despite supportive care, delay umbralisib until \leq grade 1; thereafter, resume umbralisib at next lower dose level.

Table 12: Non-Hematologic Toxicity Management		
Event Terms	CTCAE Grade	Study Agent Management Guidelines ¹

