6.3 Serious Adverse Event Reporting

A serious adverse event (SAE) is any adverse event that occurs after the initial dose of study treatment, during treatment, or within 30 days of the last dose of treatment that results in one of the following outcomes or meets at least one of the following criteria:

- Death
- Hospitalization for greater than 24 hours
- Prolonging an existing inpatient hospitalization
- A life-threatening experience (that is, immediate risk of dying)
- Persistent or significant disability/incapacity
- Congenital anomaly/birth defect
- Any suspected transmission of an infectious agent via a study agent (e.g. Prion Protein Transmitting Transmissible Spongiform Encephalopathy)
- Any confirmed occurrence of Hy's Law, defined as an ALT or AST $\geq 3 \times$ institutional ULN **AND** concurrent total bilirubin $\geq 2 \times$ institutional ULN without findings of cholestasis
- Considered significant by the investigator for any other reason

If an investigator becomes aware of an SAE that is considered related to acalabrutinib after completion of the 30-day period following the last dose of acalabrutinib, the event should also be reported as an SAE to Acerta Pharma at the contact information given below.

Previously planned (prior to signing the informed consent form) surgeries, and non-disease related elective surgeries planned during the course of the study, should not be reported as SAEs unless the underlying medical condition has worsened or appeared during the course of the study. Events that occur prior to the first administration of study medication should not be reported as SAEs.

Preplanned hospitalizations or procedures for pre-existing conditions that are already recorded in the patient's medical history at the time of study enrollment should not be considered SAEs. Hospitalization or prolongation of hospitalization without a precipitating clinical AE (e.g., for the administration of study therapy or other protocol-required procedure) should not be considered SAEs.

Important medical events that may not result in death, be life-threatening, or require hospitalization may be considered SAEs when, based on appropriate medical judgment, they may jeopardize the patient and may require medical or surgical intervention to prevent one of the outcomes listed in this definition.

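### Section 12.3 leaves asymptomatic laboratory abnormalities out of the 3-of-10 serious-toxicity count without limit, so an asymptomatic grade 3 or higher liver-test rise, or a Hy's Law case without symptoms, may not count

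*Combined protocol and SAP*

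**What the plan says.** Section 12.3 looks at the first 10 participants with at least one cycle of all three agents. If serious toxicity occurs in 3 or more of them, "this will trigger a consultation with the DSMC about stopping accrual". It counts "events that occur during the first cycle of triple therapy, unless they are clearly due to underlying disease or extraneous causes". Three kinds of event qualify: infusion-related reactions of grade 4 or higher, infections of grade 4 or higher, and other clinically significant grade 3 or higher "non-hematologic toxicity, except asymptomatic laboratory abnormalities or nausea/vomiting/diarrhea that improves with supportive care". The stated trigger probabilities are 0.07, 0.18, 0.74 and 0.83 at true rates of 10%, 15%, 35% and 40%.

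Two other places deal with liver tests.

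- Table 12 (Section 5.3) defines liver toxicity by ALT, AST and bilirubin. Its row for grade 3 or higher reads "Hold dosing of umbralisib, ublituximab, and acalabrutinib" and starts prednisone. No symptom is required.
- Section 6.3 lists among the SAE criteria "Any confirmed occurrence of Hy's Law, defined as an ALT or AST" at or above 3 times the upper limit of normal, with total bilirubin at or above 2 times the limit and no cholestasis. This too is a laboratory definition.

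**The concern.** The count in Section 12.3 is the only numeric safety trigger in the plan. If it passes over events that the protocol elsewhere treats as important enough to hold every agent or to report as an SAE, the DSMC may not be consulted when those events accumulate. The stated probabilities would then describe a narrower rate than a reader is likely to suppose.

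The window makes the liver relevant. Triple therapy starts in cycle 7, when ublituximab is added (Section 4.1). The background reports grade 3/4 ALT/AST increases in 17% of a 12-patient part of a single-agent ublituximab study (Section 2.3.3), and transaminitis of any grade in 10 of 42 participants (24%) on umbralisib plus ibrutinib (Section 2.5).

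**Working it through.** **1. Reproduce the stated figures.** Inputs from Section 12.3: n = 10, trigger at 3 or more. The trigger probability at true rate p is

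P(X ≥ 3) = 1 − [(1−p)^10 + 10p(1−p)^9 + 45p²(1−p)^8].

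- p = 0.10: 1 − (0.3487 + 0.3874 + 0.1937) = 0.0702
- p = 0.15: 1 − (0.1969 + 0.3474 + 0.2759) = 0.1798
- p = 0.35: 0.7384
- p = 0.40: 0.8327

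These round to 0.07, 0.18, 0.74 and 0.83, as stated. The arithmetic is right. The question is which events p covers.

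**2. Set the texts side by side** for a participant in cycle 7 with a grade 4 ALT rise and no symptoms.

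- Table 12: liver toxicity of grade 3 or higher; all agents held and prednisone started.
- Section 6.3: an SAE if the bilirubin criterion is also met and Hy's Law is confirmed.
- Section 12.3: an asymptomatic laboratory abnormality, hence excepted on the plain reading.

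Two details support that reading. First, Section 12.3 already confines the category to clinically significant toxicity. An exception aimed only at insignificant laboratory values would add nothing, so as worded it can remove significant ones. Second, Table 12 has asymptomatic-laboratory exceptions of its own, but they stand only in the row for other non-hematologic toxicity. The one that lets dosing continue is confined to abnormalities judged not clinically significant. The liver rows have no such exception.

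**3. Size.** Let b be the rate of toxicity that counts as written, and q the added rate of participants whose only qualifying event is an asymptomatic liver event of the kind described. Both are assumptions. The trigger probability is P(X ≥ 3) at p = b as written, and at p = b + q if these events count.

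| b | as written | q = 5% | q = 10% |
|---|---|---|---|
| 5% | 0.01 | 0.07 | 0.18 |
| 10% | 0.07 | 0.18 | 0.32 |
| 15% | 0.18 | 0.32 | 0.47 |

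For b = 10% and q = 10%, p = 0.20: 1 − (0.1074 + 0.2684 + 0.3020) = 0.322. With q = 0 nothing changes.

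**The case against.** Much can be said for the plan, and several stronger readings fail.

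- **That no grade 3-4 liver toxicity can trigger the consultation.** A reader might infer this, but the exception covers only asymptomatic abnormalities. Symptomatic, clinically significant liver toxicity of grade 3 or higher counts.
- **That the exclusion is certain.** The closing condition about improving with supportive care could be read as applying to the laboratory abnormalities too, and the list is introduced in words that need not be exhaustive. Some asymptomatic cases would then count. This weakens the claim but strengthens the request for clarity, since two assessors could score the same case differently.
- **That Section 12.3 contradicts the SAE definition.** It does not. It sets its own monitoring term, narrower than SAE throughout: it also omits grade 3 infections and grade 3 infusion reactions, which could be SAEs if the participant is hospitalized.
- **That the trigger probability would be about 0.48.** Adding an independent 17% to a 10% base gives 1 − 0.90 × 0.83 = 0.253, and P(X ≥ 3) is then 0.48. The sum is right but the input is unsuitable. The 17% comes from 12 patients with eight planned infusions and 12 months of follow-up, and is neither a one-cycle rate nor stated to be asymptomatic. In the closer study, 46 participants on ibrutinib, umbralisib and ublituximab, the most common grade 3/4 events were neutropenia (22%) and cellulitis (13%) (Section 2.5). Any grade 3/4 transaminase rise should therefore have been no more frequent than about 13% over the whole course. The 24% on umbralisib plus ibrutinib is of any grade, and the hepatitis named in Section 2.1 is attributed to idelalisib, which is not a study drug.
- **That safety oversight is blind to these events.** SAEs go to the sponsor-investigator within 1 business day (Section 6.3), Table 12 acts on each participant, and the DSMC reviews toxicity up to four times a year (Section 11.2). These remain, though none has a numeric threshold.

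It also stands that umbralisib and ublituximab are no longer supplied as of March 2023 (Section 5.5), so the rule may have no prospective use left. Liver events in cycles 1 to 6 fall outside the window whatever the exception says.

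**Conclusion.** The point holds as a gap in the definition of the count. Because the laboratory exception is not limited to abnormalities that lack clinical significance, the 3-of-10 rule can pass over asymptomatic liver events that Table 12 and Section 6.3 treat as important. No stated figure is wrong.

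The effect cannot be fixed from the documents, which give no one-cycle rate of asymptomatic grade 3-4 liver toxicity for this triplet. On an assumed 10% of other serious toxicity, and with liver events adding to that rate without overlap, an extra 5% moves the trigger probability from 0.07 to about 0.18, and an extra 10% to 0.32. The consequence is a missed or delayed consultation, not a missed automatic stop.

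**What to change.** State in Section 12.3 that the laboratory exception does not cover (a) confirmed Hy's Law cases as defined in Section 6.3, or (b) ALT, AST or bilirubin increases of grade 3 or higher for which study agents were held under Table 12. This reconciles the three places and leaves the management rules in Table 12 as they are. The same sentence should make clear whether improvement with supportive care qualifies the laboratory abnormalities or only the gastrointestinal events.

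The four probabilities stay, since they depend only on n, the threshold and the true rate. The text should say that this rate now includes the added events, and the sponsor should confirm that 3 of 10 is still the threshold wanted for it. If the first 10 participants have already been assessed, report the count with and without these events.

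The cost is small. Serum chemistry is already scheduled on days 1, 2, 8 and 15 of cycle 7 (Table 20), so no new assessments are needed. The downside is that a DSMC consultation becomes somewhat more likely.
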